1.0 PROJECT SUMMARY

BACKGROUND AND RATIONALE

Patellar tendinopathy (PT) is a common disabling overuse injury that is highly prevalent in sports, especially amongst jumping athletes. PT affects 32% of elite basketball players and may lead to considerable long-term morbidity, resulting in a negative effect on their career with up to 50% of athletes forced to quit their sport. Treatment of PT remains challenging, and no currently available conservative therapies directly address the underlying pathophysiology of tissue degeneration. We will conduct a 52-week double-blinded randomized controlled clinical study to investigate the efficacy of PRP and to determine if the intervention truly provides better improvements in pain and function and enhanced tissue healing when compared to less expensive minimally-invasive treatment options.

OBJECTIVES

The overall goal of this proposal is to find an effective treatment for PT. To achieve this, we will conduct a double-blinded randomized controlled trial (RCT) to investigate if platelet-rich plasma (PRP) is effective for treating PT (4-6). Clinical (pain and function scores) and biomechanical (knee strength) measures will be correlated with disease modification changes assessed using conventional and novel quantitative magnetic resonance imaging (MRI) and ultrasound (US) techniques.

ELIGIBILITY

This research will target adults, ages 18 to 39 years, diagnosed with chronic (>3 months) patellar tendonitis. Diagnosis will require a clinical examination consistent with PT and/or MRI or ultrasound confirmation of PT. In addition, 10 healthy/normal subjects who are not diagnosed with chronic PT will be enrolled into a control cohort.

STUDY DESIGN

Sixty-six patients with PT will be randomized to one of three study arms. Subjects in Group 1 (PRP) will receive a single US-guided (USG) injection of 5 mL autologous PRP into the patellar tendon, subjects in Group 2 (DN) will undergo USG dry needling of the patellar tendon, and subjects in Group 3 (SH) will undergo a sham control USG dry needling in the subcutaneous tissue only (not intratendon) at the level of the patellar tendon. The efficacy of the different treatment options will be assessed by pain- and function-dependent, PT-specific Victorian Institute of Sport Assessment Patella (VISA-P) quality of life scores, Tegner activity level scores, knee strength measurements, and conventional and novel MRI and US imaging at baseline, 16, 32, and 52 weeks post-treatment.

Ten subjects without PT will comprise the healthy/normal or control cohort. The control subjects will undergo the clinical and biomechanical assessments and conventional and novel MRI and US imaging during a single study visit.

REQUIRED SAMPLE SIZE

With 20 subjects, the expected power of our study based on hypothesized changes over time and the pooled SD of the changes in VISA-P scores. To allow for 10% drop out, we will recruit 22 subjects per group. Based on the estimated SD for the changes in the VISA-P scores reported in the previous study, we are conservatively inflating our pooled SD estimate. The data collected from the 10 control subjects will be used to compare normative data to the data collected from the test population.

2.0 INTRODUCTION

Patellar tendinopathy is one of the most common disabling conditions of the knee affecting both active individuals and competitive athletes (1, 2). PT is a degenerative tendon condition resulting in localized anterior knee pain affecting the proximal patellar tendon (7). The etiology of pain related to this chronic degenerative disorder remains unclear. The degenerative features of tendinopathy, however, are similarly seen in lateral epicondylitis (8), plantar fasciitis (9), and Achilles tendinopathy (10). The pathophysiology of PT is thought to be multifactorial, including overuse microtrauma, which leads to tendon disorganization and increased vulnerability to further injury and possible rupture (7). Chronic pain from PT is costly to elite athletes by reducing peak performance, forcing early career retirement, and in the later stages of life, adopting a sedentary lifestyle which leads to other chronic diseases such as hypertension and heart diseases (2). Thus, finding a reliable treatment option would change the way we approach PT and other chronic overuse injuries. Platelet-Rich Plasma: PRP is an emerging minimally invasive treatment option that uses concentrated autologous platelets, rich in healing factors (4-6). Recent exponential use of PRP has been in the area of sports-related tendon overuse injuries (5, 6, 11-13). Currently, it has been estimated that about 100,000 elite athletes are injected with PRP annually, but the frequency of use is likely under reported (14). The main growth driver came from the media's attention on well-known professional athletes reporting a quicker and durable return to activity after PRP rather than foundational evidence-based decisions from a well-designed randomized control trial (RCT). Moreover, clinicians are often faced with increasing demand by their patients for PRP, ranging from the weekend warrior to the disabled worker, without much leverage to argue for or against its use. There are only two existing but limited two-armed RCTs of PRP that have shown equivocal results in chronic overuse injuries (15-18). Despite limited scientific evidence, PRP usage has been and will continue to grow exponentially. *Therefore, rigorous clinical trials are needed to investigate the efficacy of PRP and to determine if the intervention truly provides better improvements in pain and function and enhanced tissue healing when compared to less expensive minimally-invasive treatment options.* PRP Mechanism of Action: Platelets are vital in initiating the tissue healing process (12, 19). When activated by injury, platelet alpha-granules are released to incite soft tissue healing (20). PRP augments the native healing process at the site of tissue degeneration through the action of concentrated healing growth factors such as PDGF, VEGF, FGF, and TGF- β 1 (12). Fibroblast response and collagen formation occur in the healing response phase with tenocyte development and alignment healing (12). In chronic conditions, such as PT, few circulating platelets, and therefore low growth factor concentrations, are present, especially for tendons that receive only 30% of a muscle's blood supply (21). Therefore, delivering concentrated healing growth factors may benefit hypo-vascular soft tissue structures such as tendons. Small clinical studies have reported that PRP injections for PT decrease pain, increase function and have the potential to modify diseased tendon (15-18). However, PRP has not been

rigorously evaluated as a therapy for PT. The proposed project will be the first to assess pain- and function-dependent, knee-specific quality of life and in-vivo assessment of compositional, ultrastructural, and mechanical properties of PT post-treatment with PRP in a Level 1, RCT with subject and assessor blinding. The valuable data gained will significantly add to the knowledge base of disease modifying effects of PRP for tendinopathy. Positive findings of PRP compared to control would help establish an optimal protocol for the nonsurgical management of PT. In addition, no study has assessed the correlation between novel imaging biomarkers with validated clinical outcomes in response to therapy, which would provide a powerful imaging assessment tool to objectively monitor tissue healing.

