5.3 Research Procedures: Subjects enrolled in the chronic PT cohorts will be asked to complete four study visits at baseline, 16 weeks, 32 weeks, and 52 weeks. Subjects enrolled in the control cohort will complete 1 study visit. Health questionnaires (VISA-P Tegner, medication log, side effect log) will be mailed to subjects diagnosed with chronic PT only. A table outlining research visits is below. The following research procedures will be administered:

- 5.3.1 Randomization: The 10 healthy/normal subjects will not be randomized and will not receive any injections. The subjects diagnosed with chronic patellar tendonitis will be randomized to one of three study arms. Subjects in Group 1 (PRP) will receive a single US-guided (USG) injection of 5 mL autologous PRP using a 22G, 1.5 inch needle and after 20 needle passes targeting hypoechoic and hyperemic areas within tendon and bone attachment if involved. Subjects in Group 2 (DN) will undergo USG dry needling with 20 passes using a 22G, 1.5 inch needle targeting hypoechoic and hyperemic areas within tendon and bone attachment if involved. Subjects in Group 3 (SH) will undergo a sham control USG dry needling with 20 passes using a 22G, 1.5 inch needle placed in the subcutaneous tissue only (not intratendon) at the level of the patella tendon.
- 5.3.2 PRP Preparation and Administration (randomized subjects only): At the injection session, a nurse will perform a standard antecubital blood draw (15mL) using a 15 mL syringe and an 18G needle from the PRP group at the contralateral arm. The blood draw will occur only once. The study coordinator will then place the sample in the Arthrex ACP System and spin the blood sample using a two-stage spinning: the 1st separates red blood cells from platelets, and the 2nd concentrates the platelets to yield approximately 6mL of concentrated, autologous platelets. This layer of platelet rich plasma will be placed in the syringe by the centrifuge machine. Centrifuging will be repeated if desired concentration level is not achieved, but this has not occurred clinically and we do not anticipate inadequate platelet concentration level. All blood and equipment handling will follow universal precautions.

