Dry Needling (DN) Procedure: This is a therapeutic procedure that involves the same injection procedures under ultrasound guidance as in the PRP group but no PRP will be injected inside the patellar tendon.

Sham (SH) Placebo Procedure: Same needle size is used under ultrasound guidance as in PRP and DN groups but we will not inject PRP nor place needle inside the patellar tendon. Rather, the needle will be placed in the soft tissue next to the patellar tendon.

- 5.3.3 **Blinding (randomized subjects only):** Subjects and assessors will be blinded to the subject group allocation. Subjects in the DN and SH groups will also undergo phlebotomy to maintain blinding. Subjects will be identified to study personnel using a unique study number only and results of the imaging studies will be blinded, batched, and evaluated in a randomized manner.
- 5.3.4 **Clinical and Biomechanical Assessment (see Appendix A) - All subjects:** The clinical symptoms of all subjects will be assessed using the validated pain- and function-dependent, PT-specific Victorian Institute of Sport Assessment Patella (VISA-P) quality of life score and Tegner activity level scale. Knee flexor and extensor muscle isometric torque strength will be assessed using an isokinetic dynamometer (Kiio Sensor). Patellar tendon wave speeds will be measured with an experimental device during any or all of: strength tests with the Kiio sensor, squats, vertical jumps, walking, and running. The walking/running tasks will only be performed with subjects who have experience with treadmill walking/running. The wave speed measurement device will be placed on the surface of the skin. It consists of a piezoelectric actuator that induces waves in the tendon and miniature accelerometers that track wave propagation.

5.3.5 MRI Protocol: All subjects will undergo a non-contrast MRI examination of the knee on an MR750 3T scanner (GE Healthcare, Waukesha, WI) using an 8-channel extremity coil. Subjects will be in the scanner for approximately 45 minutes.

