8.0 Statistical Considerations

A similar study involving patients with PT estimated the pooled standard deviation (SD) of the changes in VISA-P score over time to be between 15 and 19 and the minimal detectable

	N per group	Change in DN	Change in SH	Change in PRP	Pooled SD	Power (%)
20	5.5	5.5	22	10	99.9	
20	5.5	5.5	22	15	94.8	
20	5.5	5.5	22	20	75.1	
20	5.5	5.5	16.5	10	94.8	
20	5.5	5.5	16.5	20	64.2	
20	5.5	5.5	11	5	94.8	

Table 2

change in score

to be 11.1 (41). Since our subjects will have already completed physical therapy without improvement, we hypothesize that the DN and SH groups will marginally improve and that the PRP group will significantly improve on the order of 3 times the improvement of the other groups over the 1 year follow-up period. With 20 subjects, table 2 shows the expected power of our study based on hypothesized changes over time and the pooled SD of the changes in VISA-P scores. To allow for 10% drop out, we will recruit 22 subjects per group. Based on the estimated SD for

the changes in the VISA-P scores reported in the previous study, we are conservatively inflating our pooled SD estimate.

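### No contrast is named for a PRP-specific claim: PRP and dry needling share 20 intratendon passes, so PRP versus sham, or an overall three-group test, cannot separate PRP from needling

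*Combined protocol and SAP*

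**What the plan says.** Section 5.3.1 defines the arms. PRP is injected "after 20 needle passes targeting hypoechoic and hyperemic areas within tendon and bone attachment if involved". For the second arm, "Subjects in Group 2 (DN) will undergo USG dry needling with 20 passes using a 22G, 1.5 inch needle targeting hypoechoic and hyperemic areas". The sham needle is "placed in the subcutaneous tissue only (not intratendon) at the level of the patella tendon". Section 5.3.2 says of dry needling: "This is a therapeutic procedure that involves the same injection procedures under ultrasound guidance as in the PRP group". The one difference it gives is that this arm has the needle passes without the plasma.

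Aim 3.1.1 evaluates PRP through improved VISA-P, Tegner and strength results and names no comparator. The rationale in Sections 1.0 and 2.0 asks whether PRP does better than cheaper minimally invasive alternatives. Section 2.0 closes with what a good result would mean: "Positive findings of PRP compared to control would help establish an optimal protocol for the nonsurgical management of PT". The word *control* is not defined there. Sections 1.0 and 5.3.1 attach it to the sham arm, and Section 1.0 also uses it for the 10 healthy, non-randomised subjects.

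In Section 8.0, "we hypothesize that the DN and SH groups will marginally improve", while PRP is expected to improve about three times as much as the other groups. Table 2 gives power with 20 per group, and DN and SH both improve by 5.5 in every row. Section 8.0 names no test, alpha, primary contrast or multiplicity method.

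**The concern.** Intratendon needling is common to the PRP and DN arms and absent from sham. If needling helps and PRP adds nothing, PRP will still tend to beat sham, and an overall test of the three arms will still tend to reject. Neither result would show that PRP does anything. The rationale's own question, PRP against a cheaper procedure, is the PRP-versus-DN comparison. The design includes the arm needed to answer it, but the aims and the statistical section do not say that this comparison carries the claim. Table 2 also never shows what happens if DN does better than sham, although Section 5.3.2 describes DN as therapeutic. At stake is a benefit of needling being reported as a benefit of the more expensive product.

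**Working it through.** **1. What each contrast estimates.** Treat the components as additive for illustration: needling N, PRP product P, injected volume V (5 mL in Section 5.3.2; no injectate is described for DN).

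- PRP − SH = N + P + V
- PRP − DN = P + V
- DN − SH = N

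**2. Reproducing Table 2.** Inputs from Section 8.0: n = 20 per group, the tabulated mean changes and SDs. Assumed, because not stated: alpha 0.05. Method tried: one-way F test, df 2 and 57, critical F 3.159, noncentrality λ = n × Σ(mean − grand mean)² / SD².

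| DN, SH, PRP | SD | λ | F-test power | Printed |
|---|---|---|---|---|
| 5.5, 5.5, 22 | 10 | 20 × 181.5/100 = 36.3 | >99.9% | 99.9% |
| 5.5, 5.5, 22 | 15 | 20 × 181.5/225 = 16.13 | 94.8% | 94.8% |
| 5.5, 5.5, 22 | 20 | 20 × 181.5/400 = 9.08 | 75.1% | 75.1% |
| 5.5, 5.5, 16.5 | 10 | 20 × 80.67/100 = 16.13 | 94.8% | 94.8% |
| 5.5, 5.5, 16.5 | 20 | 20 × 80.67/400 = 4.03 | 39.9% | 64.2% |
| 5.5, 5.5, 11 | 5 | 20 × 20.17/25 = 16.13 | 94.8% | 94.8% |

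Five of six rows reproduce. The printed 64.2% is the F-test value at SD 15 (λ = 7.17), so that row's SD or power looks misprinted. A two-sided t test of PRP against one comparator does not fit: it gives 72.0% where 75.1% is printed.

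**3. The F test under a pure needling effect.** Let SH = 5.5 and DN = PRP = 16.5. Grand mean 12.83; Σ = 7.33² + 3.67² + 3.67² = 80.67, the same as for (5.5, 5.5, 16.5). Power is therefore identical whether PRP alone or needling alone works: 64.2%, 43.7%, 39.9% at SD 15, 19, 20. With 22 in place of 16.5, both cases give 94.8%, 79.6%, 75.1%.

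**4. Pairwise tests under the same pure needling effect.** Two-sided t test, df 38, critical t 2.024, noncentrality δ = (difference/SD) × √(n/2). PRP versus SH is significant with probability 61.8%, 43.0%, 39.6% (difference 11), or 92.4%, 76.3%, 72.0% (difference 16.5), at SD 15, 19, 20. PRP versus DN falsely favours PRP in 2.5%.

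**5. Power of PRP versus DN when PRP does add something.** Same test, 20 per arm.

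| PRP − DN | SD 15 | SD 19 | SD 20 |
|---|---|---|---|
| 16.5 (δ = 3.48, 2.75, 2.61) | 92.4% | 76.3% | 72.0% |
| 11 (δ = 2.32, 1.83, 1.74) | 61.8% | 43.0% | 39.6% |

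The 16.5 row is Table 2's 22 against 5.5. The 11 row is the threefold hypothesis (16.5 against 5.5), or equally DN 11 and PRP 22.

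**6. Partial needling effects (assumed DN values; SH 5.5, PRP 22).** With DN at 11, the F test has 88.0%, 68.3%, 63.5% power and PRP versus DN has 61.8%, 43.0%, 39.6%. With DN at 16.5, the F-test figures are the same and PRP versus DN falls to 20.4%, 14.5%, 13.6%. The overall power says little about the comparison of interest once DN exceeds sham.

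**The case against.** A reader might infer that the plan has decided to credit PRP on a win over sham. The documents do not support that. The sentence is introductory rationale, its *control* is undefined, and no decision rule appears anywhere. The plan also randomises a needling-only arm, which is the standard way to deal with this problem, and Section 8.0 expects PRP to exceed both other groups. What remains is that this expectation is not turned into a named contrast.

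A reader might also infer that PRP versus DN isolates PRP. It does not. The PRP arm receives 5 mL of fluid, up to 4 mL of it peppered along the tendon, and no matching injection is described for DN. The contrast removes the needling effect, not the volume effect.

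The probabilities in step 4 are not rates of wrong conclusions, because readers would see the DN arm as well. Simulating that case (SH 5.5, DN and PRP 16.5, 20 per arm), PRP beats sham while DN does not in only about 16% of trials at each SD. In the others where PRP wins, DN wins too and the needling explanation is visible.

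Finally, the F test is inferred from Table 2. Nothing says that it would be the only analysis, or that pairwise comparisons would not follow.

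**Conclusion.** The point holds as a gap in specification, not as a flaw in the choice of arms. PRP versus sham measures needling plus PRP, and the test that Table 2 implies has the same power under a PRP-only and a needling-only effect (64.2%, 43.7%, 39.9% at SD 15, 19, 20 for 16.5 against 5.5). No aim or statistical text says which comparison would support a PRP-specific claim. Power for the comparison that removes needling is slightly below the overall figures when DN equals sham (for example 72.0% against 75.1% at SD 20), and well below them if DN exceeds sham.

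These figures assume 20 evaluable subjects per arm, normally distributed changes with a common SD, alpha 0.05, and an F test identified from five of six rows. The SDs of 15 and 19 are the range that Section 8.0 cites, and 20 is its inflated value. DN means above 5.5 are illustrations; the documents give no needling effect.

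**What to change.** - **Sections 3.1.1 and 8.0:** name PRP versus DN on VISA-P change as the contrast required for any PRP-specific claim. Report PRP versus SH as the effect of needling plus PRP against sham.
- **Section 2.0, closing paragraph:** say which arm *control* means.
- **Section 8.0:** state the test and alpha. Give the PRP-versus-DN power from step 5, and add rows in which DN exceeds SH. Correct the SD or the power in the 64.2% row.
- **Interpretation:** note that PRP versus DN removes the needling effect but not that of the injected volume.

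The order of testing and the multiplicity method can be left to the sponsor. Requiring PRP versus DN before PRP versus SH is one option, but at 43.0% power (11 points, SD 19) the sham comparison would often go formally untested.

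The cost is wording and a few power rows; no arm, visit or procedure changes. The downside is that the stated power is slightly lower than the overall figures and a PRP-specific claim becomes harder to win.

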3.0 STUDY AIMS/STUDY OBJECTIVES

The purpose of this research is to find an effective treatment for PT that addresses the underlying pathophysiology of tissue degeneration.

3.1 Specific aims include:

- 3.1.1 To evaluate the efficacy of PRP by reporting improved pain- and function-dependent, PT-specific Victorian Institute of Sport Assessment Patella (VISA-P) quality of life scores, Tegner activity level scores, and knee strength at baseline, 16, 32, and 52 weeks post-treatment.
- 3.1.2 To demonstrate treatment-related changes in pathologic imaging features of PT using conventional MRI (thickness and T2 signal intensity) and US (thickness, echogenicity, and hyperemia).
- 3.1.3 To investigate the relationship between changes in novel quantitative MRI (single-component and bicomponent ultra-short echo-time T2* (UTE-T2*)) and US (shear wave speed (SWS), a proxy for elasticity) parameters of PT and clinical and biomechanical improvement following treatment.

4.0 SELECTION OF PATIENTS

- 4.1 Study Population: This research will enroll 10 healthy normal adults and 66 adults diagnosed with chronic patellar tendonitis.
- 4.2 Eligibility criteria (healthy/normal)
 - 4.2.1 Age between 18 and 39 years
 - 4.2.2
- 4.3 Eligibility criteria (Subjects diagnosed with chronic patellar tendonitis)
 - 4.3.1 Inclusion criteria
 - 4.3.1.1 Age between 18 and 39 years
 - 4.3.1.2 Chronic (>3 months) PT
 - 4.3.1.3 Clinical examination consistent with PT
 - 4.3.1.4 MRI or US confirmation of PT
 - 4.3.1.5 Pain score of 3 or greater on a 10-point VAS
 - 4.3.1.6 Self-report failure of supervised physical therapy

- 4.3.1.7 Self-report failure of at least 2 of the most common treatment options for PT (e.g. NSAIDs, relative rest, ice and bracing).
- 4.3.2 Exclusion criteria (All subjects)
 - 4.3.2.1 Inability to comply with study follow-up requirements
 - 4.3.2.2 History of bleeding disorders or other hematologic conditions
 - 4.3.2.3 Knee pain from other possible etiologies (e.g., degenerative joint disease, meniscal tear, ligament injury or reconstruction)
 - 4.3.2.4 Full or partial patellar tendon tear
 - 4.3.2.5 Current use of anticoagulation or immunosuppressive therapy
 - 4.3.2.6 Prior knee trauma requiring medical attention or surgery
 - 4.3.2.7 Self-reported pregnancy
 - 4.3.2.8 Worker's compensation injury
 - 4.3.2.9 Daily opioid use for pain
 - 4.3.2.10 Contraindication to MRI.
 - 4.3.2.11 Systemic diseases such as Diabetes and connective tissue diseases.
 - 4.3.2.12 Prior PRP or DN procedure.
 - 4.3.2.13 Women that are pregnant

